10.3 Appendix 3 - Additional Safety Guidance

Further Guidance on the Definition of a Serious Adverse Event (SAE)

Life threatening

‘Life-threatening’ means that the subject was at immediate risk of death from AE as it occurred or it is suspected that use or continued use of the product would result in the subject’s death. ‘Life-threatening’ does not mean that had an AE occurred in a more severe form it might have caused death (eg, hepatitis that resolved without hepatic failure).

Hospitalisation

Outpatient treatment in an emergency room is not in itself a serious AE, although the reasons for it may be (eg, bronchospasm, laryngeal edema). Hospital admissions and/or surgical operations planned before or during a study are not considered AEs if the illness or disease existed before the subject was enrolled in the study, provided that it did not deteriorate in an unexpected way during the study.

Important Medical Event or Medical Intervention

Medical and scientific judgment should be exercised in deciding whether a case is serious in situations where important medical events may not be immediately life threatening or result in death, hospitalisation, disability or incapacity but may jeopardize the subject or may require medical intervention to prevent one or more outcomes listed in the definition of serious. These should usually be considered as serious.

Simply stopping the suspect drug does not mean that it is an important medical event; medical judgment must be used.

Examples of such events are:

- Angioedema not severe enough to require intubation but requiring intravenous hydrocortisone treatment
- Hepatotoxicity caused by paracetamol (acetaminophen) overdose requiring treatment with N-acetylcysteine
- Intensive treatment in an emergency room or at home for allergic bronchospasm
- Blood dyscrasias (eg, neutropenia or anaemia requiring blood transfusion) or convulsions that do not result in hospitalisation
- Development of drug dependency or drug abuse

Assessment of Severity

Assessment of severity is one of the responsibilities of the investigator in the evaluation of AEs and SAEs. The determination of severity should be made by the investigator based upon medical judgment and the severity categories of Grade 1 to 5 as defined below.

Grade 1 (mild)	An event that is usually transient and may require only minimal treatment or therapeutic intervention. The event does not generally interfere with usual activities of daily living.
Grade 2 (moderate)	An event that is usually alleviated with additional specific therapeutic intervention. The event interferes with usual activities of daily living, causing discomfort but poses no significant or permanent risk of harm to the subject.
Grade 3 (severe)	An event that requires intensive therapeutic intervention. The event interrupts usual activities of daily living, or significantly affects the clinical status of the subject.
Grade 4 (life threatening)	An event, and/or its immediate sequelae, that is associated with an imminent risk of death.
Grade 5 (fatal)	Death (loss of life) as a result of an event.

It is important to distinguish between serious criteria and severity of an AE. Severity is a measure of intensity whereas seriousness is defined by the criteria in Section 5.2. A Grade 3 AE need not necessarily be considered an SAE. For example, a Grade 3 headache that persists for several hours may not meet the regulatory definition of an SAE and would be considered a nonserious event, whereas a Grade 2 seizure resulting in a hospital admission would be considered an SAE.

Assessment of Relationship

Relationship to Investigational Product

The investigator is required to provide an assessment of relationship of AEs and SAEs to the investigational product.

An event will be considered “not related” to use of the investigational product if any of the following tests are met:

- An unreasonable temporal relationship between administration of the investigational product and the onset of the event (eg, the event occurred either before, or too long after, administration of the investigational product for it to be considered product-related)
- A causal relationship between the investigational product and the event is biologically implausible (eg, death as a passenger in an automobile accident)
- A clearly more likely alternative explanation for the event is present (eg, typical adverse reaction to a concomitant drug and/or typical disease-related event)

Individual AE/SAE reports will be considered “related” to use of the investigational product if the “not related” criteria are not met.

“Related” implies that the event is considered to be “associated with the use of the drug” meaning that there is “a reasonable possibility” that the event may have been caused by the product under investigation (ie, there are facts, evidence, or arguments to suggest possible causation).

Relationship to Protocol Procedures

The investigator is also required to provide an assessment of relationship of SAEs to protocol procedures on the SAE Report Form. This includes nontreatment-emergent SAEs (ie, SAEs that occur prior to the administration of investigational product) as well as treatment-emergent SAEs. A protocol-related SAE may occur as a result of a procedure or intervention required during the study (eg, blood collection, washout of an existing medication). The following guidelines should be used by investigators to assess the relationship of SAEs to the protocol:

Protocol related: The event occurred due to a procedure/intervention that was described in the protocol for which there is no alternative etiology present in the subject’s medical record.

Not protocol related: The event is related to an etiology other than the procedure/intervention that was described in the protocol (the alternative etiology must be documented in the study subject’s medical record).

10.4 Appendix 4 - National Institute of Allergy and Infectious Diseases and Food Allergy and Anaphylaxis Network Guidance for Anaphylaxis Diagnosis

National Institute of Allergy and Infectious Disease (NAID) and Food Allergy and Anaphylaxis Network (FAAN) define anaphylaxis as a serious allergic reaction that is rapid in onset and may cause death. They recognise 3 categories of anaphylaxis, with criteria designated to capture from 80% of cases (category 1) to > 95% of all cases of anaphylaxis (for all 3 categories).

1. Acute onset of an illness (minutes to several hours) with involvement of the skin, mucosal tissue, or both (eg, generalised hives, pruritus or flushing, swollen lips-tongue-uvula)
AND AT LEAST ONE OF THE FOLLOWING
 - a. Respiratory compromise (eg, dyspnoea, wheeze-bronchospasm, stridor, reduced peak expiratory flow (PEF), hypoxaemia)
 - b. Reduced BP or associated symptoms of end-organ dysfunction (eg, hypotonia [collapse], syncope, incontinence)
2. Two or more of the following that occur rapidly after exposure to a likely allergen for that patient (minutes to several hours):
 - a. Involvement of the skin-mucosal tissue (eg, generalised hives, itch-flush, swollen lips-tongue-uvula)
 - b. Respiratory compromise (eg, dyspnoea, wheeze-bronchospasm, stridor, reduced PEF, hypoxaemia)
 - c. Reduced BP or associated symptoms (eg, hypotonia [collapse], syncope, incontinence)
 - d. Persistent gastrointestinal symptoms (eg, crampy abdominal pain, vomiting)
3. Reduced BP after exposure to known allergen for that patient (minutes to several hours):
 - a. Infants and children: low systolic BP (age specific) or greater than 30% decrease in systolic BP
 - b. Adults: systolic BP of less than 90 mm Hg or greater than 30% decrease from that person's baseline

10.5 Appendix 5 - Actions Required in Cases of Increases in Liver Biochemistry and Evaluation of Hy's law

Introduction

This Appendix describes the process to be followed in order to identify and appropriately report cases of Hy's Law. It is not intended to be a comprehensive guide to the management of elevated liver biochemistries.

During the course of the study the investigator will remain vigilant for increases in liver biochemistry. The investigator is responsible for determining whether a subject meets potential Hy's Law (PHL) criteria at any point during the study.

The investigator participates, together with MedImmune clinical project representatives, in review and assessment of cases meeting PHL criteria to agree whether Hy's Law (HL) criteria are met. HL criteria are met if there is no alternative explanation for the elevations in liver biochemistry other than Drug Induced Liver Injury (DILI) caused by the investigational product.

The investigator is responsible for recording data pertaining to PHL/HL cases and for reporting adverse events (AE) and serious adverse events (SAE) according to the outcome of the review and assessment in line with standard safety reporting processes.

Definitions

Potential Hy's Law (PHL)

Aspartate aminotransferase or ALT $\geq 3 \times$ upper limit of normal (ULN) together with total bilirubin (TBL) $\geq 2 \times$ ULN at any point during the study following the start of investigational product irrespective of an increase in alkaline phosphatase (ALP).

Hy's Law (HL)

Aspartate aminotransferase or ALT $\geq 3 \times$ ULN together with TBL $\geq 2 \times$ ULN, where no other reason, other than the investigational product, can be found to explain the combination of increases; eg, elevated ALP indicating cholestasis, viral hepatitis, another drug.

For PHL and HL the elevation in transaminases must precede or be coincident with (ie, on the same day) the elevation in TBL, but there is no specified timeframe within which the elevations in transaminases and TBL must occur.

Identification of Potential Hy's Law Cases

In order to identify cases of PHL it is important to perform a comprehensive review of laboratory data for any subject who meets any of the following identification criteria in isolation or in combination:

- $ALT \geq 3 \times ULN$
- $AST \geq 3 \times ULN$
- $TBL \geq 2 \times ULN$

The investigator will without delay review each new laboratory report and if the identification criteria are met will:

- Notify the sponsor study representative
- Determine whether the subject meets PHL criteria by reviewing laboratory reports from all previous visits
- Promptly enter the laboratory data into the laboratory eCRF

Follow-up

Potential Hy's Law Criteria Are Not Met

If the subject does not meet PHL criteria the investigator will:

- Inform the sponsor representative that the subject has not met PHL criteria
- Perform follow-up on subsequent laboratory results according to the guidance provided in the Clinical Study Protocol.

Potential Hy's Law Criteria Are Met

If the subject does meet PHL criteria the investigator will notify the sponsor study representative who will then inform the central study team. The Study Physician contacts the investigator, to provide guidance, discuss and agree an approach for the study subjects' follow-up and the continuous review of data. Subsequent to this contact the investigator will:

- Monitor the subject until liver biochemistry parameters and appropriate clinical symptoms and signs return to normal or baseline levels, or as long as medically indicated
- Investigate the etiology of the event and perform diagnostic investigations as discussed with the Study Physician

- Complete the Liver eCRF Modules as information becomes available
- If at any time (in consultation with the Medical Monitor) the PHL case meets serious criteria, report it as an SAE using standard reporting procedures

Review and Assessment of Potential Hy's Law Cases

The instructions in this section should be followed for all cases where PHL criteria are met.

No later than 3 weeks after the biochemistry abnormality was initially detected, the Medical Monitor will contact the investigator in order to review available data and agree on whether there is an alternative explanation for meeting PHL criteria other than DILI caused by the investigational product. The Clinical Medical Monitor and Global Safety Physician will also be involved in this review together with other subject matter experts as appropriate.

According to the outcome of the review and assessment, the investigator will follow the instructions below.

If there is an agreed alternative explanation for the ALT or AST and TBL elevations, a determination of whether the alternative explanation is an AE will be made and subsequently whether the AE meets the criteria for a SAE:

- If the alternative explanation is not an AE, record the alternative explanation on the appropriate eCRF
- If the alternative explanation is an AE/SAE, record the AE /SAE in the eCRF accordingly and follow the sponsor standard processes

If it is agreed that there is no explanation that would explain the ALT or AST and TBL elevations other than the investigational product:

- Report an SAE (report term 'Hy's Law') according to sponsor standard processes.
 - The 'Medically Important' serious criterion should be used if no other serious criteria apply
 - As there is no alternative explanation for the HL case, a causality assessment of 'related' should be assigned.

If, there is an unavoidable delay, of over 3 weeks, in obtaining the information necessary to assess whether or not the case meets the criteria for HL, then it is assumed that there is no alternative explanation until such time as an informed decision can be made:

- Report an SAE (report term ‘Potential Hy’s Law’) applying serious criteria and causality assessment as per above
- Continue follow-up and review according to agreed plan. Once the necessary supplementary information is obtained, repeat the review and assessment to determine whether HL criteria are met. Update the SAE report according to the outcome of the review

FDA Guidance for Industry (issued July 2009) ‘Drug-induced liver injury: Premarketing clinical evaluation’:

<http://www.fda.gov/downloads/Drugs/GuidanceComplianceRegulatoryInformation/Guidances/UCM174090.pdf>

[REDACTED]

[REDACTED]

[REDACTED]

[REDACTED]

[REDACTED]

[REDACTED]

[REDACTED]

[REDACTED]

[REDACTED]

[REDACTED]

[REDACTED]

[REDACTED]

[REDACTED]

[REDACTED]

[REDACTED]

[REDACTED]

[REDACTED]

[REDACTED]

[REDACTED]

[REDACTED]

[REDACTED]

[REDACTED]

[REDACTED]

[REDACTED]

[REDACTED]

[REDACTED]

[REDACTED]

[REDACTED]

[Redacted]

[Redacted]

[Redacted]

[Redacted]

[Redacted]

[Redacted]

[Redacted]

[Redacted]

[Redacted]

[REDACTED]

[REDACTED]

[REDACTED]

[REDACTED]

[REDACTED]

[REDACTED]

[REDACTED]

[REDACTED]

[REDACTED]

[REDACTED]

[Redacted text block]

[Redacted text block]

[Redacted text block]

[Redacted text block]

10.7 Appendix 7 Biological Samples

Storage, Re-use and Destruction of Biological Samples

Biological samples will be stored for a maximum of 15 years from the date of the Last Subject's Last Visit, after which they will be destroyed.

The results of biomarker research will be reported either in the CSR itself or as an addendum, or separately in a scientific report or publication. The results of this biomarker research may be pooled with biomarker data from other studies with the study drug to generate hypotheses to be tested in future research. ADA samples will be stored for up to 2 years after marketing approval.

Labelling and Shipment of Biological Samples

The principal investigator ensures that samples are labelled and shipped in accordance with the Laboratory Manual and the Biological Substance, Category B Regulations (materials containing or suspected to contain infectious substances that do not meet Category A criteria).

Any samples identified as Infectious Category A materials are not shipped and no further samples will be taken from the subject unless agreed with MedImmune and appropriate labelling, shipment and containment provisions are approved.

Chain of Custody of Biological Samples

A full chain of custody is maintained for all samples throughout their lifecycle.

The principal investigator at each study site keeps full traceability of collected biological samples from the subjects while in storage at the study site until shipment or disposal (where appropriate) and keeps documentation of receipt of arrival. The sample receiver keeps full traceability of the samples while in storage and during use until used or disposed of or until further shipment and keeps documentation of receipt of arrival.

MedImmune keeps oversight of the entire life cycle through internal procedures, monitoring of study sites and auditing of external laboratory providers.

Samples retained for further use are registered in the Translational Sciences Biorepository during the entire life cycle.

Document Name:		d5670C00011-protocol-amendment-2	
Document Title:	d5670C00011-protocol-amendment-2		
Document ID:	Doc ID-003705066		
Version Label:	1.0 Approved CURRENT LATEST		
Server Date (dd-MMM-yyyy HH:mm 'GMT'Z)	SignedBy	Meaning of Signature	
17-Oct-2017 16:56 GMT+0100	██████████	Biostatistics Approval	
17-Oct-2017 17:05 GMT+0100	██████████	Research Approval	
17-Oct-2017 17:07 GMT+0100	██████████	Clinical Operations Approval	

5 VERSION HISTORY17

LIST OF FIGURES AND TABLES

Figure 2.2-1 Study Flow Diagram6
Table 3.2-1 Analysis Populations.....8

List of Abbreviations

Abbreviation or Specialized Term	Definition
ABPM	Ambulatory blood pressure monitoring
ADA	Anti-drug antibody
AE	Adverse event
ANCOVA	Analysis of covariance
ATC	Anatomical Therapeutic Chemical
AUC	Area under the concentration-time curve
BMI	Body mass index
CGM	Continuous glucose monitoring
█	█
CV	Coefficient of variation (standard deviation/mean)
eCRF	electronic Case Report Form
ECG	Electrocardiogram
FFA	free fatty acids
█	█
GLP-1	Glucagon-like peptide-1
hr	hours
IM	Immunogenicity
ITT	Intent-to-Treat
IWRS	Interactive web response system
LOCF	Last observation carried forward
MMTT	Mixed-meal tolerance test
msec	milliseconds
PD	Pharmacodynamics
PK	Pharmacokinetics
PT	Preferred Term
SAE	Serious adverse event
SAP	Statistical analysis plan
SC	Subcutaneous
SID	Subject identification number
SOC	System Organ Class
SPP	Statistical programming plan
T2DM	Type 2 diabetes mellitus
ULN	Upper limit of normal reference range

1 INTRODUCTION

This document describes the statistical analysis methodology for protocol D5670C00011, a phase 2a study to evaluate the efficacy, safety, tolerability, and pharmacokinetics (PK) of different doses of MEDI0382 in overweight and obese subjects with Type 2 Diabetes Mellitus. The main portion of this document details the statistical summaries relating to each study objective and describes the general conventions and definitions that will be used. In addition, a set of table templates and specifications will be included in a statistical programming plan (SPP) to complement this document.

2 STUDY OVERVIEW

2.1 Study Objectives

2.1.1 Primary Study Objective(s)

To assess the effects of MEDI0382 titrated up to a dose level of 300 µg on glucose control and body weight versus placebo after 49 days of treatment (Cohort 1 only).

2.1.2 Secondary Study Objectives

- To assess the effects of MEDI0382 titrated up to a dose level of 300 µg on additional measures of glucose control and body weight versus placebo after 49 days of treatment (Cohort 1 only).
- To characterize the safety profile and tolerability of MEDI0382 titrated up to a dose level of 300 µg during dosing and follow-up (Cohorts 1 and 2).
- To characterize the PK profile and immunogenicity of 50 and 300 µg of MEDI0382 (Cohorts 1 and 2).
- To characterize the effect of 50 µg of MEDI0382 on glucose lowering versus placebo after 7 days (Cohorts 1 and 2).

2.1.3 Exploratory Study Objectives

[figure not shown]
- [REDACTED]
- To assess gastrointestinal tolerability across different titration schedules (Cohorts 1 and 2).
- To assess the effect of MEDI0382 on glucose lowering during different meals and times of the day as measured by continuous glucose monitoring (CGM) (Cohort 1 only).
- To characterize the effect of MEDI0382 on glucose lowering and weight versus placebo after 7, 14 and 49 days (Cohort 2 only).
- To assess the effect of MEDI0382 on pancreatic and incretin hormone profiles at baseline and during the mixed-meal tolerance test (MMTT) (Cohorts 1 and 2).
- To assess the effect of MEDI0382 on ketone bodies, amino acids, and free fatty acid (FFA) levels over 49 days of treatment (Cohort 1 only).

[figure not shown]
- To assess the effect of MEDI0382 on uric acid [REDACTED] (Cohort 1 only).

2.2 Study Design

This is a randomized, double-blind, placebo-controlled study to evaluate the efficacy, safety, tolerability, and PK profile of 50 and 300 µg of MEDI0382 in overweight and obese subjects with T2DM. Up to 63 subjects are planned to be enrolled across multiple study sites. The study is divided into 2 cohorts that will be recruited in parallel; for both cohorts, subjects will be consented, screened for suitability, and randomized within 60 days if eligible. A total of 39 subjects will be randomized to Cohort 1, and 24 subjects will be randomized to Cohort 2. Cohort 1 will evaluate the efficacy, safety, tolerability, and PK of MEDI0382 when titrated up in weekly intervals from 50 to 300 µg and administered over 49 days. Cohort 2 will explore an alternative 2-week titration schedule, and will provide additional information on the PK profile and glucose-lowering efficacy of 50 µg MEDI0382 [REDACTED]. Each dose is administered as an SC injection each morning according to the dosing schedule is presented below:

Figure 2.2-1 Study Flow Diagram

2.3 Treatment Assignment and Blinding

An interactive web response system (IWRS) will be used for randomization to a treatment group and assignment of blinded investigational product kit numbers. A subject is considered randomized when the IWRS provides the assignment of blinded investigational product kit numbers for the subject.

In Cohort 1, subjects will be randomized using a ratio of 2:1 to one of 2 treatment arms to receive either MEDI0382, titrated from 50 µg up to 300 µg according to a fixed schedule, or placebo for 49 days.

In Cohort 2, subjects will be randomized using a ratio of 3:1 to receive either MEDI0382, titrated from 50 µg up to 300 µg according to a different fixed schedule, or placebo for 49 days.

This is a double-blind study in which MEDI0382 and placebo are identically labeled and indistinguishable in appearance so that neither the subject nor any of the investigator or sponsor staff who are involved in the treatment or clinical evaluation of the subjects or data analysis will be aware of the treatment received (ICH E9).

2.4 Sample Size

For Cohort 1, 26 subjects in the MEDI0382 arm and 13 subjects in the placebo arm will provide 97% power to detect 28% glucose AUC change-from-baseline difference between MEDI0382 300 µg and placebo, assuming a standard deviation of 20%. It will also provide 85% power to detect 2.3% difference of percentage change of body weight versus placebo, assuming a standard deviation of 2.2%. From the two cohorts, the combined 44 subjects in

the MEDI0382 arms and 19 subjects in the placebo arms can also provide 80% power to detect 12% glucose AUC change-from-baseline difference between MEDI0382 50 µg and placebo at Day 7.

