For Cohort 1, 26 subjects in the MEDI0382 arm and 13 subjects in the placebo arm will provide 97% power to detect a 28% glucose AUC change-from-baseline difference between MEDI0382 300 µg and placebo, assuming a standard deviation of 20%. It will also provide 85% power to detect a 2.3% difference of percentage change of body weight from baseline versus placebo, assuming a standard deviation of 2.2%.

Under the conservative assumption that the two endpoints are independent, the overall power that hypotheses for both endpoints are met is over 80%. From the 2 cohorts, the combined 44 subjects in the MEDI0382 arms and 19 subjects in the placebo arms can also provide 80% power to detect a 12% glucose AUC change-from-baseline difference between MEDI0382 50 µg and placebo at Day 7.

Statistical analyses:

The efficacy analysis will be based on the Intent-to-treat population. The coprimary efficacy endpoints of percentage glucose AUC change and percentage weight change from baseline to 49 days will be compared between the MEDI0382 and placebo arms using an analysis of covariance (ANCOVA) model, adjusting for treatment and measurement at baseline. A similar ANCOVA model will also be used for other continuous endpoints. For the other proportion-related endpoints, a logistic regression model will be used with fixed effects of treatment and baseline measurement.

Safety analyses:

The safety analyses will be based on the As-treated population. Safety data, such as vital signs, clinical laboratory data, ECG, and physical examination findings will be descriptively summarised at each time point by treatment period.

Pharmacokinetic analysis and immunogenicity:

Pharmacokinetic parameters such as MEDI0382 C_{max} and area under the concentration-time curve from 0 to infinity ($AUC_{(0-inf)}$) will be evaluated from plasma concentration-time data for MEDI0382 at 50 and 300 µg. Descriptive statistics including mean, standard deviations, median, minimum, and maximum will be generated for all PK parameters for MEDI0382 at each dose level separately. Samples confirmed positive for ADA will be tested and analysed for antibody titre and reported. ADA incidence rate and titre will be tabulated for each treatment.

Interim analysis: An interim analysis of PK data only will be performed following last subject last dose.

TABLE OF CONTENTS

PROTOCOL SYNOPSIS	2
LIST OF ABBREVIATIONS	12
1 INTRODUCTION	14
1.1 Disease Background.....	14
1.2 MEDI0382 Background	14

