1.4 Summary of Clinical Experience

In prior clinical experience (Cohort 4 of Study D5670C00002), treatment with MEDI0382 up to 200 µg from a start dose of 100 µg for 41 days with 2 titration steps of 4 days duration was associated with a mean reduction from baseline in body weight of 4.1% (90% confidence interval [CI] -4.9, -3.4) in MEDI0382-treated subjects versus 1.8% (90% CI -2.5, -1.0) in placebo, $p < 0.001$, and a mean reduction from baseline in glucose AUC_{MMT,4h} of 32.8% (90% CI -37.0, -28.6) vs 10.2% (90% CI -14.1, -6.2) in placebo, $p \leq 0.0001$. MEDI0382 was shown to have an acceptable safety profile. There were no unexpected safety signals and no increases in systolic or diastolic BP across the study. In Cohort 4, dosing over 41 days was associated with increased gastrointestinal (GI) adverse events (AEs) with 40 AEs of vomiting observed in 8 (32%) of subjects; however, the number of events diminished in frequency with dose up-titration ($n = 19$ at 100 µg, $n = 10$ at 150 µg, and $n = 11$ at 200 µg).

Extrapolating from these results it is anticipated that MEDI0382 will achieve GLP-1 receptor agonist-like glucose control, but with the potential for disease-modifying weight loss of greater than 10% of body weight over one year.

Refer to the current MEDI0382 IB for a complete summary of clinical information.

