3.2.3.3 Exploratory Endpoints

GLP-1 analogues are established to cause increased GI side-effects which are most pronounced in the early phases of treatment (Meier, 2012). The mechanisms underlying these symptoms are multifactorial and related to PK and effects on [REDACTED] and vomiting centers of the brain (area postrema) (Orskov et al, 1996). An added dimension of complexity here is that tolerance to the effects of GLP-1 receptor agonism on [REDACTED] may develop with short-term treatment (Nauck et al, 2011). In attempts to improve GI tolerability in this drug class, both dose up-titration (Victoza, 2014) and lengthening of titration intervals from between 1 to 4 weeks have been utilised (Exenatide, 2016). In a prior Phase 1/2 study (Study D5670C00002), subjects dosed with MEDI0382 titrated in 4-day intervals from 100 µg up to 200 µg across 41 days reported mild to moderate nausea (13/25, 52%) and vomiting (8/25, 32%); however, the number of nausea and vomiting events diminished in frequency with dose up-titration (n = 19 at 100 µg, n = 10 at 150 µg, and n = 11 at 200 µg) and in most cases, events were noted to occur within 3 days of a dose up-titration step. In Cohorts 5 and 6 of Study D5670C00002, a comparison of different dose up-titration steps was made: 100 µg → 150 µg → 200 µg → 300 µg (Cohort 5; n = 11) versus 100 µg → 200 µg → 300 µg (Cohort 6; n = 12) with 5-day up-titration steps in between. The percentage of subjects reporting nausea was lower with an intermediate 150 µg dose up-titration step between 100 and 200 µg (27% vs 42%); however, the percentage of subjects with vomiting was in fact higher in this group (27% vs 8%). These results and the prior clinical experience with GLP-1 analogues imply that further modulation of the titration schedule may help to minimise GI side-effects experienced with MEDI0382. To investigate different titration schedules, Cohort 1 of this study will test a lower starting dose of MEDI0382 (50 µg) than has been previously tested in overweight and obese subjects with T2DM, and with longer up-titration steps (7 days). Cohort 2 will run in parallel with Cohort 1

and will test up-titration of MEDI0382 every 2 weeks in order to assess if this further minimises GI AEs.

[REDACTED]

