3 STATISTICAL METHODS

3.1 General Considerations

Data will be presented in data listings sorted by cohort and treatment, subject number and date collected, where appropriate. Tabular summaries will be presented by cohort and treatment group. Categorical data will be summarized by the number and percentage of subjects within each category. In general, continuous variables will be summarized by descriptive statistics including mean, standard deviation, median, minimum, and maximum.

The last observation carried forward (LOCF) will be used in efficacy and pharmacodynamics (PD) endpoints analyses unless otherwise specified. Baseline values will be defined as the last valid assessment prior to the first administration of study treatment unless otherwise specified.

All statistical tests will be 2-sided at an alpha = 0.1 significance level unless stated otherwise. There will be no adjustment for multiplicity.

Data analyses will be performed using SAS[®] version 9.3 or higher (SAS Institute Inc., Cary, NC).

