3.4.2.2 Secondary Efficacy Analyses

All analyses will be performed at the 0.05 (2-tailed) significance level unless otherwise specified.

The changes from baseline in HbA1c, fasting plasma glucose, and body weight will be analyzed using an ANCOVA with an effect for treatment and the corresponding baseline measure as a covariate. The pre-meal plasma glucose values from the MMTT are used for the fasting plasma glucose values. The proportion of subjects who have a >5% decrease in body weight will be analyzed with logistic regression with treatment effect and the baseline weight as a covariate.

The percent change in MMTT glucose AUC from baseline to Day 7, including data from both cohorts, will be analyzed with an ANCOVA with treatment effect and the baseline value used as a covariate.

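### Is the 80% power stated for the pooled Day 7 comparison of 50 µg with placebo wrong, given that no standard deviation is attached to it?

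*SAP*

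**What the plan says.** SAP 2.4 makes three power claims. For Cohort 1 (26 vs 13) it gives 97% power for a 28-point difference in glucose AUC change, "assuming a standard deviation of 20" percent, and 85% power for a 2.3-point difference in body-weight change with an SD of 2.2%. For the two cohorts together (44 vs 19) it says the study "can also provide 80% power to detect 12% glucose AUC change-from-baseline difference", specified as the contrast of 50 µg with placebo at Day 7. No SD or test level stands beside this third claim. The sample-size paragraph of the protocol synopsis says the same ("80% power to detect a 12% glucose AUC change-from-baseline difference"), again without an SD.

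The test level is set elsewhere in the SAP. Section 3.1 gives a default: "All statistical tests will be 2-sided at an alpha = 0.1 significance level unless stated otherwise". Section 3.4.2.2, which covers the Day 7 analysis, overrides it: "All analyses will be performed at the 0.05 (2-tailed) significance level unless otherwise specified". The Day 7 analysis is an ANCOVA with treatment and baseline AUC.

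**The concern.** A reader of SAP 2.4 who meets a glucose AUC claim with no SD will naturally carry down the 20% from the first sentence. The third claim then fails: power is about 58%, and the chance of missing a true 12-point effect is about 42% instead of 20%.

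This would matter to some degree. Superior glucose control at 50 µg after 7 days is a named secondary hypothesis (protocol 1.7.2), and protocol 3.2.1 says there is no efficacy information on repeat dosing below 100 µg. If power were overstated, a non-significant Day 7 result could be read as stronger evidence against 50 µg than it is. SAP 2.4 alone does not tell the reader which SD was used.

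**Working it through.** **Method.** Two-sample t-test power from the noncentral t distribution, with df = n1 + n2 − 2, standard error SE = SD × √(1/n1 + 1/n2), and noncentrality = difference / SE. All results are at two-sided 0.05 unless stated.

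**Step 1: reproduce the figures that come with an SD (SAP 2.4, 26 vs 13, df 37, critical t 2.026).** √(1/26 + 1/13) = 0.3397.
- Body weight: SE = 2.2 × 0.3397 = 0.747; noncentrality 2.3/0.747 = 3.08; power 85.0% (stated 85%).
- Day 49 glucose AUC: SE = 20 × 0.3397 = 6.79; noncentrality 28/6.79 = 4.12; power 98.0% (stated 97%).

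At two-sided 0.10 the weight figure would be 91.6%, so the section appears to have been planned at 0.05.

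**Step 2: the Day 7 claim (44 vs 19, difference 12, df 61, critical t 2.000).** √(1/44 + 1/19) = 0.2745. With the borrowed SD of 20%, SE = 20 × 0.2745 = 5.49, noncentrality 12/5.49 = 2.19, and power is 57.6%. At the general 0.10 level it would be 69.7%. Neither is 80%.

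**Step 3: which SD gives 80%?** Solving for the SD gives 15.36%: SE = 15.36 × 0.2745 = 4.22, noncentrality 12/4.22 = 2.85, power 80%. With the SD held at 20%, 80% power would need a difference of 15.6 points.

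**Step 4: the other variability figure in the documents.** Protocol 1.4 reports the prior study's reduction in glucose AUC as "32.8% (90% CI -37.0, -28.6) vs 10.2% (90% CI -14.1, -6.2) in placebo". The half-width for the active arm is (37.0 − 28.6)/2 = 4.2. The number analysed is not given there; I assume 25, the denominator of the adverse-event percentages in protocol 3.2.3.3 ("reported mild to moderate nausea (13/25, 52%) and vomiting (8/25, 32" percent). The implied SD is 4.2 × √25 / 1.711 = 12.3%. That gives SE = 12.3 × 0.2745 = 3.38, noncentrality 3.55 and power 93.8%. This is a rough guide only. It describes one arm, at up to 200 µg over 41 days, and the interval may be model-adjusted.

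**Step 5: the range.**

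| Day 7 SD | Power, two-sided 0.05 |
|---|---|
| 12.3% (inferred from the prior study) | 94% |
| 15% | 82% |
| 15.4% | 80% |
| 18% | 67% |
| 20% (stated for Day 49, 300 µg) | 58% |

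The SD needed for the stated 80% lies between the two figures that can be drawn from the visible text.

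**Step 6: baseline adjustment.** If 20% were an unadjusted SD, a correlation of 0.64 between baseline and outcome would reduce the residual SD to 20 × √(1 − 0.64²) = 15.4%, and power would again be 80%. No correlation is stated, and the weight figure in Step 1 reproduces without any such reduction, so this is a possibility and no more.

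**The case for a change.** The strongest case for acting is that the section sets its own standard. Two of its three claims state an SD and come out close to the printed figure by an ordinary t-test. The third omits the SD, and with the only glucose AUC SD on the page it drops by 22 points (80 − 58). Neither that SD nor the one inferred from the prior study returns 80%. Stating the SD would cost one sentence, and it would tell a reader of a negative Day 7 result whether the planned miss rate was nearer 6% or 42%.

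The omission stands: SAP 2.4 carries no redaction and does not give the SD. The rest is weaker. The 20% is tied by its own sentence to 300 µg in Cohort 1, and nothing extends it to 50 µg at Day 7. That neither figure gives exactly 80% does not count against the claim when the two fall on either side of it. The test level is not open, because SAP 3.4.2.2 fixes it. The protocol's Section 4.8.2 on sample size and power, named in the Amendment 1 summary, is blacked out in the public copy, so the SD and its source may well be recorded there. Once the data are in, a non-significant result will be read from the estimate, its confidence interval and the SD observed at Day 7; planned power adds little to that.

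**Conclusion.** The concern does not hold as an arithmetic error. The 80% cannot be verified from the visible text, but it is not shown to be wrong. It is what 44 vs 19 subjects give for a 12-point difference at two-sided 0.05 with an SD of about 15.4%, within the 12.3% to 20% (94% to 58% power) that the documents allow. The 58% applies only if 20% was also meant for Day 7, which the SAP does not say. The 94% end rests on the assumption of 25 subjects in the prior-study arm and on that interval being unadjusted.

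What is left is a planning assumption not written down for one secondary comparison in a Phase 2a study with no multiplicity adjustment. Co-primary power, the sample size, the Day 7 ANCOVA and its test level would be the same whatever the SD was. A statistician who has the sponsor's sample-size file can supply the figure when asked. No change to the plan follows.
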